### 2.2 Secondary Objectives

The following secondary objectives will be assessed overall and according to various subgroups of interest, unless otherwise specified:

- To estimate in adult patients with early-stage EC or GEJC initiating adjuvant nivolumab treatment:
  - DFS and DFS rates in subgroups of interest only
  - $\circ$   $\,$  Median overall survival (OS) and OS rates  $\,$
  - Distant metastasis-free survival (DMFS) and DMFS rates
- To describe treatment patterns of adjuvant nivolumab (dosing, regimen, indication, treatment rationale, treatment duration, modifications in relation to the management of AE, reasons for treatment discontinuation/cessation) and subsequent therapy (regimen, duration) and time to next treatment (TTNT)
- To estimate from initiation of subsequent treatment, in patients that receive subsequent treatment(s) following adjuvant nivolumab discontinuation:
  - OS and OS rates
  - Progression free survival 2 (PFS2) and PFS2 rates
  - Overall response rate (ORR)
- To describe disease recurrence patterns in patients with a recurrence, including time to recurrence, type of recurrence (local/regional vs metastatic), and PRS
- To describe sociodemographic and clinical characteristics, and treatment history
- To describe incidence and severity of AEs and SAEs in relation to nivolumab

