## 3 STUDY DESIGN

### 3.1 Overview of Study Design

This is a non-interventional, prospective, multinational, multicenter, post-marketing observational study designed to describe the real-world effectiveness and patterns of use of adjuvant nivolumab in patients with early stage (Stage II/III) EC or GEJC. This study will be conducted in the US and Germany will collect data available from patients' medical files and other items routinely collected during disease management in clinical practice and patient-reported outcomes (PRO) related to treatment satisfaction and quality of life.

This study is strictly observational and does not result in interference with standard medical care; thus, it will not impact the treatment of study participants. Prescriptions of nivolumab will be at

the sole discretion of the treating physician. Patients are to be enrolled into this noninterventional, primary data collection study no earlier than the decision to initiate treatment with nivolumab and no later than the first dose of nivolumab treatment. It is mandatory that the treating physician's decision to start treatment with nivolumab for early-stage EC or GECJ is taken independently and before the decision to invite the patient to participate in the study. Day 0 corresponds to the day of nivolumab initiation (administration of the first dose of treatment). The local investigator is responsible for the exact procedures of administration of nivolumab, and concomitant medications and therapies deemed necessary for the supportive care and safety of the patients.

Once the decision to prescribe nivolumab is taken by the medical team/physicians according to usual practice, patients will be screened for selection criteria. If the patient meets all inclusion criteria and none of the exclusion criteria, the investigator should then invite the patient to participate in the study and collect their consent to participate. Enrollment in the study is then clearly distinguished from the therapeutic decision to initiate nivolumab.

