Physicians will be asked to enroll eligible patients consecutively until the total expected study sample size is reached or the end of the enrollment period (whichever occurs first). The enrollment period is anticipated to last approximately 18 months. The follow-up time will vary between patients due to the nature of the study with ongoing enrollment; patients will be followed for up to 42 months for the first patient in and up to 24 months for the last patient in. Patients will be followed until the end of study period, death, lost to follow-up, or withdrawal, whichever comes first. Patients will be censored at last record or assessment for those lost to follow-up.

Assessment schedules will be performed according to routine local clinical practice. Data collection and data entry by sites will start at Day 0 (baseline, i.e., the day of nivolumab initiation), and at the following months with a time window of +/- 15 days: months 3, 6, 9, 12, 18, 24, 30, 36, and 42 counted relative to treatment initiation (two and 3.5 years after nivolumab initiation for the first and last patient in, respectively). As this is a non-interventional study, no visits or measurements will be made mandatory by the protocol, and data collection at these prespecified timepoints will only take place if the patient visits the site as per standard of care. Investigators or qualified research staff should collect data from the visit nearest to the time point.

Sites will receive fees to compensate for the time spent for data collection and entry into eCRFs. Since the study is intended to reflect usual clinical practice, physicians will not be required to perform any mandatory patient assessments or laboratory tests that they would not ordinarily do in treating their patients. This protocol requires that sites submit all relevant documentation to their respective institutional review board (IRB) or Ethics Committee (EC) and obtain approval or acknowledgment of notification, depending on the local requirements. Participating patients must provide written informed consent prior to study commencement, and they have the right to withdraw from the study at any time. This study will be conducted with support of a clinical research organization (CRO).

An overview of study design and data collection is shown in Figure 1.

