PFS2	Time-to-event	Time between initiation of subsequent treatment and date of disease progression or death if occurred before progression. In case of censored event, the duration of response is censored on the date of last tumor assessment or enrollment (whichever occurs last)
PFS2 rates	Continuous	PFS2 rates are defined as the probability that a patient is alive and presents no signs of disease progression at specific time points, following subsequent treatment initiation.
ORR of subsequent treatment	Continuous	Total number of patients with CR or PR to subsequent treatment divided by the total number of patients.

Abbreviations: CR = Complete Response; DFS = Disease-Free Survival; DMFS = Distant Metastasis-Free Survival; OS = Overall Survival; ORR = Overall Response Rate; PFS2 = Progression-Free Survival 2; PR = Partial Response; PRS = Post-Recurrence Survival

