## 4.1.3 Analysis Plan for Secondary Objectives

## 4.1.3.1 Secondary Effectiveness Outcomes

The analysis of OS and DMFS for all nivolumab patients and OS and PFS2 for patients that receive subsequent treatment following nivolumab treatment discontinuation will be performed following a similar procedure as for DFS (see Section 4.1.2) and will be estimated and plotted using the KM estimator overall and by subgroup of interests.

- Median DFS in subgroup of interest (overall DFS is assessed a primary outcome) and DFS rates will be estimated and reported along with the corresponding two-sided 95% Cis
- Median OS with the corresponding two-sided 95% CIs will be reported. OS rates will be estimated and reported along with the corresponding two-sided 95% CIs.

- Median DMFS and the corresponding two-sided 95% CIs will be estimated. DMFS rates will be estimated and the corresponding two-sided 95% CIs will be reported.
- Median PFS2 and the corresponding two-sided 95% CIs will be estimated. PFS2 rates will be estimated and the corresponding two-sided 95% CIs will be reported.
- Median ORR the corresponding two-sided 95% CIs
- Where adequate follow-up data is available median DFS, OS, PFS2, DMFS and ORR with their corresponding two-sided 95% CIs will be estimated in subgroup of interests (see section 4.1.1.4) as described for the overall population.

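### The PFS2 censoring rule can give negative times because its fallback date, enrollment, always precedes the start of subsequent treatment

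*Protocol*

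**What the plan says.** Table 2 (section 3.5.1.1) defines PFS2 as "Time between initiation of subsequent treatment and date of disease progression or death if occurred before progression". The same row then gives the censoring rule: "In case of censored event, the duration of response is censored on the date of last tumor assessment or enrollment (whichever occurs last".

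Three other statements fix the order of the dates:

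- Section 3.1 places enrollment "no earlier than the decision to initiate treatment with nivolumab and no later than the first dose of nivolumab treatment".
- Section 2.2 limits PFS2, OS after subsequent treatment and ORR to patients treated after nivolumab has stopped: "To estimate from initiation of subsequent treatment, in patients that receive subsequent treatment(s) following adjuvant nivolumab discontinuation".
- Section 3.1 also states that "no visits or measurements will be made mandatory by the protocol", so tumor assessments follow routine practice only.

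Section 4.1.1.2 lists PFS2 among the Kaplan-Meier outcomes, with numbers at risk and a descriptive summary of the times that includes the minimum, quartiles and maximum.

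In the same block of Table 2, ORR is defined as "Total number of patients with CR or PR to subsequent treatment divided by the total number of patients". Section 4.1.3.1 plans to report "Median ORR the corresponding two-sided 95% CIs".

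**The concern.** A censoring date has to lie on or after the time origin. The rule offers two dates and takes the later one, which protects against a negative time only if at least one of them cannot precede the origin. Enrollment could do that for an endpoint measured from the first nivolumab dose and enrolled on that day. It cannot do so for an endpoint that starts only after nivolumab has been stopped and another treatment begun. The mention of duration of response adds to the difficulty, since Table 2 defines no such outcome.

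At stake is whether PFS2 can be computed for every patient in its own population. An analyst who meets negative times must drop them, reset them or report them as they are. The protocol endorses none of these, and each gives a different N and a different time summary.

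**Working it through.** The protocol gives no figure for PFS2, so there is nothing to reproduce. The check is one of date order.

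**Inputs**

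- Origin: start of subsequent treatment (Table 2, PFS2 row).
- Censoring date: the later of last tumor assessment and enrollment (same row).
- Enrollment: on or before the first nivolumab dose (section 3.1).
- Population: patients who start another treatment after nivolumab discontinuation (section 2.2).

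**Step 1, formula.** Censored PFS2 time = max(last tumor assessment, enrollment) - start of subsequent treatment.

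**Step 2, order of dates.** Enrollment ≤ first nivolumab dose < start of subsequent treatment. The enrollment term is therefore negative for every patient in the PFS2 population. The result is zero or more only if a tumor assessment falls on or after the start of subsequent treatment.

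**Step 3, who is affected.** A patient who progresses or dies is an event with a non-negative time, scanned or not. The rule fails only for a patient who is alive, progression-free and has no tumor assessment on or after the start of subsequent treatment. Since no assessment is mandatory, this is foreseeable, for example when the last scan on file is the one that showed the recurrence.

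**Step 4, illustration with assumed dates.** Enrollment on day 0, last scan on day 300, no later scan, no event; one month = 30.4375 days.

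| Gap from scan to start (days) | Start (day) | Time under the rule (months) | Time if enrollment is the last date (months) | Time with a floor at the start date |
|---|---|---|---|---|
| 14 | 314 | (300 - 314)/30.4375 = -0.46 | (0 - 314)/30.4375 = -10.3 | 0 |
| 28 | 328 | (300 - 328)/30.4375 = -0.92 | (0 - 328)/30.4375 = -10.8 | 0 |
| 42 | 342 | (300 - 342)/30.4375 = -1.38 | (0 - 342)/30.4375 = -11.2 | 0 |

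The fourth column drops the day-300 scan and needs a patient with no assessment recorded after enrollment. It is an extreme case, because Table 3 collects the imaging used to assess recurrence at all visits.

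**Step 5, effect on the Kaplan-Meier estimate.** The estimate is S(t) = Π(1 - d_j/n_j), where n_j counts patients whose time is at least t_j. A patient whose time is zero or negative enters no n_j at any positive event time, so the curve, median and interval are the same whether that patient is dropped or censored at time 0. Censoring at day 1 differs only if an event falls within the first day. What does change is the number of patients in the analysis, the number initially at risk, the number censored, and the minimum and possibly the quartiles of the time summary.

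**Step 6, other rules in the protocol.** OS after subsequent treatment has the same origin in Table 2 but censors at the date last known alive, which cannot precede it. The general rule in section 3.1, censoring at the last record or assessment, covers only patients lost to follow-up and sets no explicit floor at the PFS2 origin. No other section repairs the rule.

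**The case against.** The strongest reply is that this is a wording defect in a secondary outcome of a study that section 4.1.1 calls purely descriptive, and that the same section assigns censoring methods to the SAP. The reply holds as to severity. It does not make the sentence right: the protocol is not silent here but states a rule that fails for a foreseeable group, and a SAP would have to depart from it.

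Three stronger readings are tempting and are not supported.

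- *Every patient without a scan on subsequent treatment gets a negative time.* Those who die or have progression recorded are events with valid times. Only censored patients are affected.
- *Dropping the negative times biases the PFS2 curve, and a floor cures it.* By step 5 the curve is essentially the same either way. Any selection on having been scanned remains under the fix.
- *ORR is diluted severalfold because its denominator is all enrolled patients.* The row does not qualify its total, but it sits under the Table 2 block heading for patients who received subsequent treatment after nivolumab, and section 2.2 sets the same restriction. The natural reading is the subsequent-treatment population. Nor do the documents give a reason to narrow it further to patients treated for recurrent disease.

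The planned median ORR is a slip in a list of medians. Table 2 defines ORR as a ratio of counts, so nobody could compute a median from it.

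**Conclusion.** The PFS2 censoring rule is wrong as written. Enrollment precedes the origin for every patient in the population, so the fallback never works, and a censored patient without a later tumor assessment receives an impossible time. The rule also names the wrong quantity.

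Severity is minor to moderate. How many patients are affected depends on how many start subsequent treatment and how many of those are neither scanned afterwards nor have an event, and the protocol gives neither figure. The negative values shown rest on assumed dates. The damage is confined to the reported counts and time summary for PFS2. The conclusion assumes that the protocol text stands alone; a SAP not shown here may already set a floor.

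**What to change.** In the PFS2 row of Table 2, replace the censoring sentence with: patients without progression or death are censored for PFS2 at the last tumor assessment on or after the start of subsequent treatment or, if there is none, at that start date (time 0 or day 1, one convention to be stated). This also removes the reference to duration of response. Report how many patients are censored at the start date, since they add nothing to the curve and their number shows how far PFS2 rests on patients who were scanned.

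As a minor wording correction in section 4.1.3.1, replace the median ORR, including its repeat in the subgroup bullet, with the ORR as a proportion and a binomial 95% CI among patients who received subsequent treatment. Repeating that population in the ORR row of Table 2 would prevent misreading.

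The cost is a few sentences. No new data are needed, because Table 3 already collects the start date of subsequent treatment and the dates of imaging assessments.

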## 3.5.1.2 Treatment Pattern Outcomes

The variables used to evaluate treatment patterns, changes in treatment, and outcomes throughout the follow-up period are described in **Table 3**. Data necessary to derive these outcomes will be collected if available. In this study, Day 0 is defined as the date of initiation of nivolumab treatment.

All baseline characteristics such as treatment or disease history will be collected retrospectively. As this data will be assessed before the date and time of the first dose of adjuvant nivolumab treatment, if the time (onset time of event or evaluation time) is missing or not collected, the following definitions will apply:

- Pre-treatment diseases/conditions will be defined as diseases/conditions with an onset date prior to but not including the day of the first dose of adjuvant nivolumab.
- Baseline measurements are defined as measurements at nivolumab initiation (i.e., Day 0) or prior to the day of the first dose of nivolumab. If there are multiple valid assessments, the assessment closest to the day (and time, if collected) of the first dose of nivolumab treatment will be used as the baseline measurements. If multiple assessments are collected on the same date (and time, if collected), the assessment with the latest database entry date (and time, if collected) will be considered as baseline.

Variables	Definition	Timing
Cancer treatment history		
Type of prior therapy	Type of therapies received prior to initiation of nivolumab treatment (e.g., radiotherapy, chemotherapy, targeted therapy, systemic treatment, platinum-based therapy) and details (if applicable, e.g., regimens, dosing)	
Start and end dates for each prior therapy	Date of initiation and discontinuation of each prior therapy	
EC/GEJC stage when treated with prior therapy	EC/GEJC Stage (i.e., I, II or III) and staging using Tumor (T), node (N), and metastasis (M) (TNM) system during prior therapy	Baseline
Indication for prior therapy	Treatment indication	
Prior therapy setting	Neoadjuvant/adjuvant/palliative	
Surgery for cancer	Information on cancer surgery including, date, type, resection status (e.g., R0, R1), results, and setting	
Concomitant medications during prior therapy	Other medications received during prior cancer treatment	
Nivolumab treatment		

Table 3. Treatment Pattern Outcomes Definition and Timing

Variables	Definition	Timing
EC/GEJC stage at initiation	EC/GEJC Stage (i.e., II or III) and staging using TNM system at nivolumab treatment initiation	
Indication for nivolumab	Treatment indication	Day 0
Start date of nivolumab treatment	Date of nivolumab initiation	Day 0
Time from surgery to nivolumab initiation	Time from date of surgery to treatment nivolumab initiation	
Dosing	Dosing (i.e., frequency, dose, and number of administered doses), dose modifications (reasons for dose/frequency changes, interruption, and discontinuation)	All visits 
Other treatment(s)	-	
Concomitant type of treatment or therapies and details	Type of treatment or therapies receive in parallel of nivolumab treatment and details (e.g., medications, radiotherapy, chemotherapy, systemic therapy, or surgical treatment)	
Systemic treatment details, if applicable	
 
Type (Immunotherapy, targeted therapy, other)
 
Drug names
 
Dosage
 
Number of received administrations
 
Start date, end date
 
	All visits 
At completion/discontinuation of nivol	umab treatment	
End date of nivolumab treatment	Date of nivolumab treatment completion/discontinuation	
Permanent discontinuation of nivolumab	Permanent discontinuation is defined as 3 missed infusions. If nivolumab is restarted after 3 missed infusions, it should be considered as a new line of therapy (LOT).	
Temporary discontinuation	Temporary discontinuation is defined as 1 or 2 skipped infusions.	
Reason(s) for discontinuation	Reasons: death, disease progression, study drug related toxicity, non-study drug related toxicity, patient request, pregnancy, lost to follow-up, other	
Time-to-treatment discontinuation	Time from date of nivolumab treatment initiation to date of last infusion + 2 or 4 (if administered every 4 weeks) weeks (first 'missed' infusion), or the date of failure from a competing risk (e.g., death)	All visits 
Subsequent treatment after nivolumab discontinuation	
 
Yes/No
 
Type of treatment and details
 
Start date, end date
 
	
TTNT	
 
Start date, end date of nivolumab treatment
 
Start date, end date of subsequent treatment(s)
 
	
Modifications in relation to the management of AEs	Any changes in nivolumab treatment related to the management of AEs	
Treatment outcomes		
Disease stage after nivolumab treatment	EC/GEJC stage (i.e., II or III) and stage using TNM system	

Variables	Definition	Timing
Recurrence	
 
Yes/No
 
Date of recurrence
 
Type of recurrence (i.e., local, regional, distant)
 
	
Disease progression	
 
Yes/No (as assessed by investigator or RECIST criteria)
 
Date of disease progression
 
	
Medical imaging test to assess treatment outcomesMedical imaging test used to assess recurrence of progression (e.g., computed tomography (CT) / r resonance imaging (MRI), Conventional X-ray, I details including method of assessment (i.e., by I or as assessed by the treating physician) and date assessment		All visits 
Death	

Yes/No

Date of death

Cause of death

	

 Data will be collected at visits Day 0, and Months 3, 6, 9, 12, 18, 24, 30, 36, and 42.

Abbreviations: AEs = adverse events; CT = computed tomography; EC = esophageal cancer; GEJC = gastroesophageal junction cancer; MRI = magnetic resonance imaging; PET = positron emission tomography; RECIST= Response evaluation criteria in solid tumors; TNM=Tumor Node Metastasis

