DFS	Time-to-event	Time between initiation of nivolumab treatment and the first date of recurrence (local, regional, or distant from the primary resected site) or death from any causes, whichever occurs first, as assessed by the investigator prior to subsequent anti-cancer therapy.
DFS rates	Continuous	DFS rates are defined as the probability that a patient is alive and presents no signs of recurrence at specific time points, following adjuvant nivolumab initiation.
08	Time-to-event	Time between initiation of nivolumab treatment until date of death due to any cause. Patients who are alive at last visit will be censored on date last known to be alive.
OS rates	Continuous	OS rates are defined as the probability that a patient is alive at specific time points, following adjuvant nivolumab initiation.
DMFS	Time-to-event	Time between initiation of nivolumab treatment and date of appearance of distant metastasis or death from any causes, whichever occurs first, as assessed by the investigator prior to subsequent anti-cancer therapy.
DMFS rates	Continuous	DFS rates are defined as the probability that a patient is alive and presents no signs of metastasis at specific time points, following adjuvant nivolumab initiation.
Time to recurrence	Continuous	Time between initiation of nivolumab treatment and the first date of recurrence.
Recurrence rates	Categorical	Recurrence rates are defined as disease recurrence (i.e., local/regional, metastatic) at specific time points, following adjuvant nivolumab initiation.
PRS	Time-to-event	PRS is defined as the interval from the date of any recurrence to the date of death from any cause. Patients who are alive at last visit will be censored on date last known to be alive.
Effectiveness outcomes in pati discontinuation:	ients that receive s	ubsequent treatment(s) following adjuvant nivolumab
OS of subsequent treatment	Time-to-event	Time between initiation of subsequent treatment until date of death due to any cause. Patients who are alive at last visit will be censored on date last known to be alive.
OS rates of subsequent treatment	Continuous	OS rates are defined as the probability that a patient is alive at specific time points, following subsequent treatment initiation.

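### Table 3 makes any nivolumab restart after 3 missed infusions a new line of therapy, so recurrence-free patients who resume their adjuvant course fall into TTNT and the subsequent-treatment OS, PFS2 and ORR

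*Protocol*

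**What the plan says.** Protocol Section 3.5.1.2, Table 3, sorts dosing gaps by the number of infusions missed: "Temporary discontinuation is defined as 1 or 2 skipped infusions" and "Permanent discontinuation is defined as 3 missed infusions". It then says of a later restart: "If nivolumab is restarted after 3 missed infusions, it should be considered as a new line of therapy (LOT"). Neither the reason for the gap nor disease status enters the rule. The next rows of the table list subsequent treatment after nivolumab discontinuation, and TTNT, which is built from the nivolumab and subsequent-treatment dates.

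Section 2.2 sets the population for the later endpoints: "To estimate from initiation of subsequent treatment, in patients that receive subsequent treatment(s) following adjuvant nivolumab discontinuation". In Section 3.5.1.1, Table 2, PFS2 is "Time between initiation of subsequent treatment and date of disease progression or death if occurred before progression" and ORR is "Total number of patients with CR or PR to subsequent treatment divided by the total number of patients". None of these asks for a recurrence or for measurable disease.

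The DFS row of Table 2 counts recurrence or death, "whichever occurs first, as assessed by the investigator prior to subsequent anti-cancer therapy". The DMFS row carries the same qualifier.

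**The concern.** Take a resected patient with no recurrence who misses three infusions, for example because of an adverse event, and then resumes the same adjuvant course. Under Table 3 this patient has permanently discontinued and then begun a new line. The protocol offers no category for that line other than subsequent treatment, and nothing excludes it.

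Three secondary results are then hard to interpret:

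- **TTNT** records the resumption of the same drug as the next treatment.
- **ORR** gains a patient in the denominator who cannot reach the numerator.
- **OS and PFS2 from subsequent treatment** combine patients treated for recurrence with patients still disease-free. For the latter, PFS2 would time a first recurrence.

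A further question concerns DFS and DMFS: does a first recurrence after the restart still fall before subsequent anti-cancer therapy?

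The trigger also counts infusions, not time, so the same gap is classed differently on the two dosing intervals that Table 3 recognises.

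**Working it through.** The plan gives no figure on this point to reproduce, and it states no restart rate. The working is a comparison of definitions, one exact calculation and two illustrations with assumed inputs.

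**1. Definitions side by side.** Three missed infusions (Table 3) → permanent discontinuation → restart is a new line → treatment after nivolumab discontinuation (Section 2.2) → TTNT date and membership of the OS, PFS2 and ORR set (Tables 2 and 3). No step refers to recurrence. The link from new line to subsequent treatment is the natural reading, but it is not stated.

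**2. Schedule.** The time-to-discontinuation row in Table 3 uses both intervals: "Time from date of nivolumab treatment initiation to date of last infusion + 2 or 4 (if administered every 4 weeks) weeks (first 'missed' infusion"). With interval *q* weeks and *m* missed infusions, the dose-to-dose gap is *q* × (*m* + 1).

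- 2-weekly, *m* = 3: 2 × 4 = 8 weeks.
- 4-weekly, *m* = 3: 4 × 4 = 16 weeks.
- A 12-week gap means 12/2 − 1 = 5 missed infusions (permanent) on 2-weekly dosing, and 12/4 − 1 = 2 missed (temporary) on 4-weekly dosing.

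**3. Effect on primary DFS if restarters were censored.** The protocol does not state such censoring; this only bounds the effect.

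- From the protocol (Section 4.2): two-year DFS 40%, and n = 285 before the drop-out allowance.
- Assumed: exponential DFS with rate −ln(0.40)/24 per month; 2%, 5% or 10% of patients marked to restart, doing so at month 6 if still disease-free; hazard after restart 1, 1.5 or 0.67 times the original. There were 400 simulated studies per setting. The first three result columns are for an unchanged hazard.

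| Restart share | Mean restarters | Their DFS events by month 24 | 95% half-width | Bias at 24 months, hazard 1.5× or 0.67× |
|---|---|---|---|---|
| 0% | 0 | 0 | 5.7 points | none |
| 2% | 4.49 | 2.22 | 5.7 | about 0.2 points |
| 5% | 11.29 | 5.76 | 5.8 | 0.5 to 0.6 |
| 10% | 22.60 | 11.08 | 5.9 | 1.0 to 1.2 |

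If the hazard does not change after restart, the estimate stays near 40%.

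**4. Effect on ORR.** Further assumptions: 80% of DFS events are recurrences, 70% of those are treated, and true ORR is 30%.

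- Treated recurrences: 285 × 0.60 × 0.80 × 0.70 = 95.76. Responders: 0.30 × 95.76 = 28.73.
- Some restarters later recur and are treated, so they are already among the 95.76. Overlap = their events × 0.80 × 0.70: 2.22 × 0.56 = 1.24; 5.76 × 0.56 = 3.23; 11.08 × 0.56 = 6.20.
- Set size = 95.76 + restarters − overlap: 99.01, 103.82 and 112.16.
- Share of restarters in the set: 4.49/99.01 = 5%; 11.29/103.82 = 11%; 22.60/112.16 = 20%.
- If ORR is judged on the first subsequent treatment, every restarter is a non-responder. Reported ORR = 0.30 × (1 − share) = 28.6%, 26.7% and 24.0%.
- If a response to any later line counts, reported ORR = 28.73/set size = 29.0%, 27.7% and 25.6%.

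Using 314 patients in place of 285 leaves these percentages unchanged, because both groups scale together.

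**The case against.** A reader might go further and infer that these patients leave DFS follow-up and that their later recurrences are lost from the primary endpoint. The protocol does not support that. It would need two unstated steps: that a new line of therapy is subsequent anti-cancer therapy, and that the Table 2 qualifier means censoring when it starts. Against it:

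- Section 3.1 ends follow-up only at end of study, death, loss to follow-up or withdrawal.
- The synopsis definition of DFS has no therapy qualifier.
- Table 1 counts a relapse detected at any time in follow-up after nivolumab initiation.
- Section 4.1.1 assigns censoring to the SAP.

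What remains for DFS and DMFS is unclear wording.

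It can also be said that the line-of-therapy sentence sits among treatment-pattern variables, that the subsequent-treatment and TTNT rows do not mention it, and that deriving such variables is commonly SAP work. This is fair as far as it goes: the protocol never equates the two terms. But it has already fixed the line-of-therapy rule without limiting its scope, and has defined the later endpoints broadly enough to take the restart in. A programmer following the text would include these patients.

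The magnitude rests on assumed inputs, and counting infusions instead of weeks is a choice open to the sponsor. Both points stand. The study is also descriptive, with no hypothesis tests.

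**Conclusion.** The point holds for the secondary endpoints. As written, the definitions place recurrence-free patients who resume adjuvant nivolumab after three missed infusions in TTNT and in the subsequent-treatment OS, PFS2 and ORR. The direction for ORR is certain: such a restart can only lower it. Under the assumed inputs the loss is about 1 to 6 points from a true 30%. OS and PFS2 become a mixture of two prognoses; the documents do not allow that to be sized.

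For DFS and DMFS the finding is only that the wording leaves a first recurrence after restart unclear. Even if restart were a censoring point, the effect on the two-year DFS rate would be about 1 point at a 10% restart share and about 0.2 points at 2%, and then only if prognosis changes after the restart.

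The schedule dependence is exact and needs no assumption. The correction should be made, but the primary result does not hang on it.

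**What to change.** Reconcile Tables 2 and 3 with one sentence, limited to endpoint derivation: nivolumab resumed with no documented recurrence in between is described as a restart, and is not a subsequent (anti-cancer) treatment for DFS, DMFS, TTNT, or the subsequent-treatment OS, PFS2 and ORR.

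Leave the Section 2.2 population as it is. Limiting PFS2 and ORR to therapy given after recurrence would change that stated objective, drop patients who switch to another drug without recurrence, and leave OS describing a different cohort from PFS2 and ORR. Leave all clinical handling of missed infusions unchanged.

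The sentence removes the schedule dependence from these endpoints for recurrence-free restarts. It remains in the descriptive counts of temporary and permanent discontinuation, where reporting the gap in weeks would make it visible.

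Cost: one definition edit. Recurrence dates and treatment start and end dates are already collected under Table 3. The downside is a slightly smaller subsequent-treatment cohort.
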